7) All fertile males and females must be using effective contraception during treatment and during 14 days after treatment end.

Exclusion criteria

The subject must be excluded from participating in the trial if the subject:

- 1) Is taking or plans to take any prohibited medications as per DAA Product Information or herbal supplements, including but not limited to St. John’s Wort (*Hypericum perforatum*) within 2 weeks of Baseline.
- 2) Is currently using or intends to use barbiturates.
- 3) Is a female and is pregnant or breast-feeding, or expecting to conceive or donate eggs from Baseline and continue throughout treatment, and after the last dose of study medication (as per the regimen requirements), or longer if dictated by local regulations.
- 4) Has any condition or pre-study laboratory abnormality, ECG abnormality or history of any illness, which, in the opinion of the investigator, might confound the results of the study or pose additional risk in administering the study drugs to the subject.
- 5) Had a life-threatening SAE during the screening period.
- 6) Has exclusionary laboratory values as listed below:

Laboratory Assessment	Value
Haemoglobin	< 9.5 g/dL for both males and females
Platelets	< 75 x 10 ³ /μL
Serum albumin	< 3.0 g/dL

	
9) Has Child Pugh-B or C decompensated cirrhosis.
 
10) Has previous HCV treatment-experience.
 
11) Has ongoing severe psychiatric disease as judged by the treating physician.
 
12) Has frequent injecting drug use that is judged by the treating physician to compromise treatment safety.
 
14) Is unable or unwilling to provide informed consent or abide by the requirements of the study.
 
15) Is Hepatitis B surface antigen (HBsAg) positive.

Study design	
The study will be conducted as a phase IV, open-label single arm multicentre trial.
 
A total of 150 participants with chronic hepatitis C virus infection genotype 1 or 4 with recent injecting drug use or receiving OST will be enrolled.
 
The study consists of a treatment phase of 12 weeks and a follow up phase of up to 3 years. Participants will be followed up every 3 months for the first year and every 6 months in year's 2-3 to evaluate treatment response and reinfection.

Treatment of participants	
Participants with chronic hepatitis C infection genotype 1 or 4 will receive 12 weeks of open-label elbasvir/grazoprevir (50mg/100mg) in a once daily fixed combination.

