Interferon-free and ribavirin-free DAA HCV therapy with elbasvir/grazoprevir will lead to SVR12 >90% among PWID with recent injecting drug use or receiving OST and chronic HCV genotype 1 or 4 infection.

Secondary Hypothesis

The incidence of HCV reinfection following successful interferon-free and ribavirin-free DAA therapy with elbasvir/grazoprevir will be <8 per 100 p-yrs among people with recent injecting drug use or receiving OST.

Primary Objective

To evaluate the proportion of patients with undetectable HCV RNA at 12 weeks post end of treatment (SVR12) following interferon-free and ribavirin-free DAA therapy with elbasvir/grazoprevir among PWID with recent injecting drug use or receiving OST and chronic HCV genotype 1 or 4 infection and evaluate demographic and clinical predictors of non-response.

Secondary Objective

To evaluate the rate of HCV reinfection up to three years following interferon-free and ribavirin-free DAA therapy with elbasvir/grazoprevir.

Exploratory Objectives

- 1) To evaluate factors associated with SVR12 (e.g. drug use at baseline and during therapy, adherence);
- 2) To evaluate the adherence to therapy and associated factors;
- 3) To evaluate safety and tolerability;
- 4) To evaluate injecting risk behaviours during and following HCV treatment;
- 5) To evaluate HCV phylogenetic clustering and molecular epidemiology;
- 6) To evaluate the prevalence of resistance associated substitutions;
- 7) To determine the sensitivity and specificity of the Xpert® HCV Viral Load assay for HCV RNA detection in samples collected by finger-stick capillary whole-blood.

3. Participant population

Participants will be recruited from tertiary, drug and alcohol and primary health care services in Sydney, Australia.

All patients must be eligible for PBS treatment with elbasvir/grazoprevir as per the prescribing guidelines. In addition the following inclusion and exclusion criteria apply.

Inclusion criteria

- 1) Participants have voluntarily signed the informed consent form.
- 2) Be ≥ 18 years of age on day of signing informed consent form.
- 3) Have chronic HCV genotype 1 or 4 infection (defined as detectable HCV RNA).
- 4) Recent injecting drug use (previous 6 months) or receiving opioid substitution therapy.
- 5) HIV-1 infected subjects enrolled in the study must meet the following criteria:

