12) Has frequent injecting drug use that is judged by the treating physician to compromise treatment safety.

13) Is unable or unwilling to provide informed consent or abide by the requirements of the study.

15) Is Hepatitis B surface antigen (HBsAg) positive.

4. Study design

The primary objective of this project is to evaluate the proportion of patients with undetectable HCV RNA at 12 weeks post end of treatment (SVR12) following therapy with elbasvir/grazoprevir among PWID with recent injecting drug use or receiving OST and chronic HCV genotype 1 or 4 infection and evaluate demographic and clinical predictors of non-response. The secondary objective of this project is to evaluate the rate of HCV reinfection up to three years following treatment among PWID with recent injecting drug use.

A prospective, observational cohort design will be used to enrol patients with chronic HCV and recent injecting drug use (injecting drug use in the previous six months) attending tertiary, drug and alcohol and primary health care services. Persons with chronic HCV genotype 1 or 4 and recent injecting drug use (in the previous 6 months) or receiving OST will receive therapy with elbasvir/grazoprevir.

[figure not shown]

Figure 1. Cohort Study Schema

The study consists of a treatment phase (12 weeks) and a follow-up phase (up to 3 years) where participants will be followed every 3 months for the first year and every 6 months in years 2-3 to evaluate treatment response and reinfection.

5. Treatment of participants

It is estimated that a total 150 participants with HCV genotype 1 or 4 will be treated (approximately 100 in 2017 and 50 in 2018). All participants will be treated with a ribavirin-free regimen of elbasvir/grazoprevir for 12 weeks (all treatment-naïve) as per the recommended indication.

Therapy with elbasvir/grazoprevir will be administered within indication utilising PBS drug therefore a Clinical Trials Notification (CTN) is not required.

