9.3 Future use of biological samples

After the samples have been analysed for the study endpoints as specified in the protocol, remaining samples will be stored for use in future Human Research Ethics Committee approved hepatitis C related research. Additional consent will not be sought for this storage and future use. It is not optional. Subjects not wishing to have their samples stored or used in future hepatitis C related research will not be eligible to participate in this study.

10. Statistics

The statistical team and investigators at the Kirby Institute will be responsible for analysing the study data.

Primary Objective: To evaluate the proportion of patients with undetectable HCV RNA at 12 weeks post end of treatment (SVR12) following elbasvir/grazoprevir therapy among PWID with recent injecting drug use or receiving OST and chronic HCV genotype 1 or 4 infection and evaluate demographic and clinical predictors of non-response.

Hypothesis: *Elbasvir/grazoprevir therapy will lead to SVR12 >90% among PWID with recent injecting drug use or receiving OST and chronic HCV genotype 1 or 4 infection.*

Outcome: The primary endpoint for this aim is the proportion of participants with a treatment response (measured by SVR, undetectable HCV RNA 12 weeks after the completion of therapy).

Statistical analysis: The proportion of people with a response to HCV therapy will be evaluated. Factors associated with treatment response (as measured by SVR) will be assessed by univariate and multivariate logistic regression analyses. Factors hypothesized to be associated with HCV treatment response will be assessed including: sociodemographic factors (housing and education), injecting behaviours (recent injecting drug use prior to and during therapy and type of drug injected), and clinical factors (opioid substitution treatment, HCV genotype, fibrosis stage).

Sample Size: Assuming an overall SVR of 90% (135 of 150), the 95% confidence interval around this estimate will be 84.0% to 94.3%. This study will have robust power to examine the effect of treatment setting on SVR: e.g. 80% power to detect an odds ratio of 0.39 or 2.59 or more extreme (with alpha=0.05) for a variable that is 50% prevalent.

Secondary Objective: Estimate incidence and predictors of HCV reinfection after successful elbasvir/grazoprevir.

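### The claim of robust power for the effect of treatment setting on SVR does not follow from the plan's own 90% SVR, and the comparison it supports is neither specified nor protected against differences between sites

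*Combined protocol and SAP*

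**What the plan says.** Section 10 (Statistics, Primary Objective, Sample Size) and the Statistics row of the synopsis carry the same two statements. The first concerns precision: "Assuming an overall SVR of 90% (135 of 150), the 95% confidence interval around this estimate will be 84.0% to 94.3" percent. The second concerns power: "This study will have robust power to examine the effect of treatment setting on SVR". Its worked example claims "80% power to detect an odds ratio of 0.39 or 2.59 or more extreme (with alpha=0.05"), "for a variable that is 50% prevalent".

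Treatment setting means the type of recruiting service. Section 3 says: "Participants will be recruited from tertiary, drug and alcohol and primary health care services in Sydney, Australia". The synopsis describes the design: "The study will be conducted as a phase IV, open-label single arm multicentre trial".

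Under Statistical analysis in section 10, factors associated with SVR "will be assessed by univariate and multivariate logistic regression analyses". The factors named are housing, education, recent injecting before and during therapy, type of drug injected, opioid substitution treatment, HCV genotype and fibrosis stage. The list is open-ended, but neither setting nor site is on it. The documents contain no site term, random effect, clustered variance or design effect.

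**The concern.** Three things in the power sentence do not fit the rest of the plan.

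- **The arithmetic.** With 90% SVR there are only about 15 failures among 150 participants. That is very little information for detecting an odds ratio near 2.6.
- **The specification.** Setting is the only effect that the SVR sample-size text names, yet it is not among the factors to be analysed. It has three categories, while the example is for a binary factor.
- **The unit.** Everyone at a service has the same setting, so a contrast between settings is a contrast between groups of sites. Sites can differ for reasons unrelated to the model of care. The clearest documented one is the exclusion criterion left to each physician: "Has frequent injecting drug use that is judged by the treating physician to compromise treatment safety".

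Predictors of non-response are part of the primary objective. A reader who trusts the sentence could take a null setting result as evidence of equivalence between models of care, when the study had little chance of seeing a difference. Equally, a difference due to one clinic's patient selection could be credited to its setting.

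**Working it through.** **Inputs from the documents.** N = 150; overall SVR 90% (135 responders, 15 failures); factor prevalence 50%, so 75 versus 75; odds ratio (OR) 2.59 or 0.39; alpha 0.05. Sidedness is not stated; two-sided is assumed because both directions are given.

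**1. The plan's confidence interval.** The Clopper-Pearson interval for 135/150 is 84.0% to 94.3%. This reproduces.

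**2. The plan's power figure.** For two groups of n = 75 with proportions p1 and p2, mean p and difference d:

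power = Φ[(d − 1.96·s0)/s1], where s0 = √(2p(1−p)/n) and s1 = √(p1(1−p1)/n + p2(1−p2)/n).

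At OR 2.59 with overall SVR 90%, the two groups have SVR 85.9% and 94.1%. Then d = 0.0812, s0 = 0.0490 and s1 = 0.0485, so power = Φ[(0.0812 − 0.0960)/0.0485] = Φ(−0.31) = 38%.

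| Reading | SVR in the two groups | Two-sided power |
|---|---|---|
| OR 2.59, overall SVR 90% | 85.9% vs 94.1% | 38% |
| OR 0.39, overall SVR 90% | 94.0% vs 86.0% | 37% |
| OR 2.59, reference SVR 90% | 90% vs 95.9% | 29% |
| OR 0.39, reference SVR 90% | 90% vs 77.8% | 53% |
| OR 2.59, reference SVR 50% | 50% vs 72.1% | 80% |
| OR 0.39, reference SVR 50% | 50% vs 28.1% | 79% |

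For OR 2.59 at overall SVR 90%, a Wald logistic formula gives 42% and Fisher's exact test 29%. The highest one-sided value among the 90% readings is 65%. No reading based on 90% reaches 80%.

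The stated odds ratios are recovered almost exactly with a reference SVR of 50%: the detectable ORs at N = 150 are then 2.588 and 0.386. With overall SVR 90%, the OR detectable with 80% power is 6.13, or 0.16 in the other direction (83.2% vs 96.8%). Reaching 80% power at OR 2.59 with overall SVR 90% would need about 428 participants (284 to 592 across the four 90% readings, without continuity correction).

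**3. Allowance for site.** The documents give neither the number of sites nor an intra-site correlation (ICC). Assumed ranges: 6 to 10 equal sites (m = 25 to 15 participants each) and ICC 0.01 to 0.05. Because setting is constant within a service, the full design effect DE = 1 + (m − 1)·ICC applies.

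| | m = 15, ICC 0.01 | m = 25, ICC 0.05 |
|---|---|---|
| DE | 1 + 14 × 0.01 = 1.14 | 1 + 24 × 0.05 = 2.20 |
| True SE / reported SE = √DE | 1.07 | 1.48 |
| Effective N = 150/DE | 132 | 68 |
| Real error of a 5% test = 2[1 − Φ(1.96/√DE)] | 6.6% | 18.6% |
| Power at OR 2.59, overall SVR 90% | 34% | 20% |

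With ICC = 0, DE = 1 and power stays at 38%.

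**The case against.** The strongest reply is that no planned model contains setting. The objective speaks of demographic and clinical predictors, setting appears in no objective, and the power statement is given as an example for a generic binary factor. A contrast such as tertiary versus community would be binary. A reader might infer that the plan will report site differences as a setting effect with falsely narrow intervals. The documents do not support that as a certainty: it follows only if setting is added to the open list and analysed by the logistic regression described. With about 15 failures the interval would be wide in any case.

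A reader might also infer that the trial has only a handful of clinics, or that sites are known to differ through their local assays and dispensing. Neither is established. The number of sites is not stated, and front matter was removed from the text available. Section 9.1 assigns stored EDTA plasma, shipped to a central laboratory, to endpoint analysis, although local testing is also scheduled. Section 8 gives one dispensing rule for all sites. Physician discretion over frequent injecting is the one clearly documented source. The upper ICC of 0.05 implies a between-site standard deviation of √(0.05 × 0.9 × 0.1) = 6.7 percentage points, which nothing in the documents supports or refutes.

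Modelling site is fragile too. At 90% SVR the chance that at least one site has no failures is 1 − (1 − 0.9^25)^6 = 36% with 6 sites of 25, and 1 − (1 − 0.9^15)^10 = 90% with 10 sites of 15.

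These objections make the clustering point conditional and limit the remedy. They do not rescue the power sentence, which names setting and fails even with fully independent participants.

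**Conclusion.** The concern holds in this form. The sentence attributes to the design a property it lacks. On the plan's own 90% SVR, two-sided power at an odds ratio of 2.59 is about 38%, with a range of 29% to 53% over the readings that use 90%. That result assumes a 75/75 split and needs no assumption about sites. That a 50% reference SVR was used is inferred from the match; the documents do not show the calculation.

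Clustering by site is a further, conditional reduction and not the main fault. If setting is analysed by the planned regression, between-site variation would be absorbed into the setting effect and its interval would be too narrow. Under the assumed 6 to 10 sites and ICC of 0.01 to 0.05, the real error of a nominal 5% test is about 7% to 19% and power is about 34% to 20%. The true size is unknown and could be nil.

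It would be wrong to read this as undermining the main result: the overall SVR12 proportion remains the primary estimate and is not altered by this point.

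**What to change.** 1. In section 10 and the synopsis, delete the robust-power sentence or recalculate it at 90% SVR. Recalculated, it would give a detectable odds ratio of about 6.1 or 0.16 for a binary factor present in half the participants, before any allowance for site.
2. State that SVR12 by treatment setting is a descriptive comparison, and define the setting categories.
3. Tabulate SVR12 by setting, and by site within setting.
4. If a setting odds ratio is reported, give it an interval that accounts for site, for example a cluster-robust variance with a small-sample correction, and note that about 15 failures may make it unstable. Fixed site effects are not an option, because they are collinear with setting.

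The cost is a change of wording in two places and one or two tables, provided the recruiting service is recorded for each participant. The downside is wider intervals and a more modest claim about setting.

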Study procedures	
Refer to the Schedule of Assessments and Study Procedures (Section 6)

Statistics	
Primary Objective: To evaluate the proportion of patients with undetectable HCV RNA at 12 weeks post end of treatment (SVR12) following elbasvir/grazoprevir therapy among PWID with recent injecting drug use or receiving OST and chronic HCV genotype 1 or 4 infection and evaluate demographic and clinical predictors of non-response.
 
Assuming an overall SVR of 90% (135 of 150), the 95% confidence interval around this estimate will be 84.0% to 94.3%. This study will have robust power to examine the effect of treatment setting on SVR: e.g. 80% power to detect an odds ratio of 0.39 or 2.59 or more extreme (with alpha=0.05)

for a variable that is 50% prevalent.

Secondary Objective: Estimate incidence and predictors of HCV reinfection after successful elbasvir/grazoprevir.

Schedule of Assessments

Assessment / Procedure	Screen	Baseline	W4	Safety	Study Treatment (weeks)	Follow-up (weeks)							
						24	36	48	60	84	108	132	156
Study weeks	-6 to 0	0	4	8	12 (ETR)	24 (SVR12)	36 (FU1)	48 (FU2)	60 (FU3)	84 (FU4)	108 (FU5)	132 (FU6)	156 (FU7)
Study Days	-42 to 0	0	28	56	84	168	252	336	420	588	756	924	1092
Visit Window (Days)			+/- 7	+/- 7	+/- 14	+/- 14	+/- 14	+/- 14	+/- 14	+/- 14	+/- 14	+/- 14	+/- 14
Informed consent, medical history	x												
Vital signs & physical measurements	x	x											
HCV-RNA testing (Local Laboratory)	x ^a		x ^a		x	x	x ^d						
HCV genotyping (Local Laboratory)	x												
Behavioural survey	x												
Abbreviated behavioural survey		x			x	x	x	x	x	x	x	x	x
Adherence survey and pill count			x	x	x								
Health outcomes survey (EQ-5D)	x				x	x							
Liver function tests/ Full blood count/ Biochemistry	x	x		x ^c	x	x							
HIV & HBV serology	x												
Fibroscan	x												
Pregnancy Test	x	x	x	x	x	x ^f							
Serious Adverse Events		x	x	x	x	x ^e							
Concomitant medication	x	x			x								
Research Sample (10 mL EDTA plasma and Whole Blood)	x ^b	x ^b	x	x	x	x	x	x	x	x	x	x	x
HCV sequencing/resistance testing (tested at Central lab using 10ml of research sample)						x ^g							
Finger-stick point-of-care HCV RNA testing (sub-study sites only)	x	x	x			x	x	x	x	x	x	x	x

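### The stated 80% power for an odds ratio of 0.39 or 2.59 on SVR12 does not fit the plan's own 90% SVR, at which unadjusted power is about 38%

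*Combined protocol and SAP*

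**What the plan says.** The design enrols 150 people: "A total of 150 participants with chronic hepatitis C virus infection genotype 1 or 4 with recent injecting drug use or receiving OST will be" … (synopsis, Study design). The primary objective has two parts, to estimate the SVR12 proportion and to "evaluate demographic and clinical predictors of non-response" (Section 2, repeated in the synopsis and Sections 4 and 10).

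Under the primary objective in Section 10, the Sample Size paragraph first gives precision: "Assuming an overall SVR of 90% (135 of 150), the 95% confidence interval around this estimate will be 84.0% to 94.3"%. It then turns to the predictor analysis: "This study will have robust power to examine the effect of treatment setting on SVR", illustrated by "80% power to detect an odds ratio of 0.39 or 2.59 or more extreme (with alpha=0.05) for a variable that is 50% prevalent". The Statistics row of the synopsis carries the same two sentences.

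The planned analysis is univariate and multivariate logistic regression. The power statement gives no response rate other than the 90% in the sentence before it, and it names no test, sidedness or formula.

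**The concern.** For a binary outcome, the power to detect a given odds ratio depends strongly on how common the outcome is. At 90% SVR only 15 of the 150 participants are expected to be non-responders, and these 15 carry most of the information about predictors. An odds ratio of 2.59 at 80% power looks too small for so few events.

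What is at stake is how the predictor results are read. A reader who trusts the sentence would expect to find an odds ratio of 2.59 in 8 of 10 such studies. That reader could then take a null result for treatment setting, OST or recent injecting as evidence against an effect of that size.

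**Working it through.** **Inputs from the plan.** N = 150; overall SVR 90%; odds ratio (OR) 0.39 or 2.59; "with alpha=0.05"; "for a variable that is 50% prevalent", hence n = 75 per group. Two-sided testing is an assumption, because sidedness is not stated.

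**Step 1: the precision figure.** The exact (Clopper-Pearson) 95% interval for 135/150 is 84.04% to 94.29%. This matches the plan.

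**Step 2: formula.** For two proportions p1 and p2, with mean m = (p1 + p2)/2:

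Power = Φ{ [ |p2 − p1| − 1.96·√(2m(1−m)/n) ] / √[ (p1(1−p1) + p2(1−p2))/n ] }

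**Step 3: power at the plan's 90%.** Solve (p1 + p2)/2 = 0.90 with [p2/(1−p2)]/[p1/(1−p1)] = 2.59. This gives p1 = 0.8594 and p2 = 0.9406.

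- Expected non-responders: 75 × 0.1406 = 10.5 and 75 × 0.0594 = 4.5.
- Difference: 0.0812.
- Null standard error: √(2 × 0.90 × 0.10/75) = 0.0490.
- Alternative standard error: √[(0.8594 × 0.1406 + 0.9406 × 0.0594)/75] = 0.0485.
- Power = Φ[(0.0812 − 1.96 × 0.0490)/0.0485] = Φ(−0.306) = **38.0%**.
- For OR 0.39 the same steps give 37.4%.

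**Step 4: other tests and readings at 90%, 75 per group.**

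| Reading | OR 2.59 | OR 0.39 |
|---|---|---|
| 90% overall, two-sided, normal approximation | 38.0% | 37.4% |
| 90% overall, exact chi-square | 38.9% | 38.3% |
| 90% overall, logistic likelihood-ratio test by enumeration | 39.2% | – |
| 90% overall, Fisher | 29.2% | – |
| 90% overall, one-sided | 50.5% | 49.9% |
| 90% in the reference group, two-sided | 28.9% (90.0% vs 95.9%) | 52.8% (90.0% vs 77.8%) |
| 90% in the reference group, one-sided | 40.6% | 65.2% |

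None reaches 80%. Even 150 per group, which is not the design, gives 65.1% for OR 2.59.

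**Step 5: where 80% would hold.** Power for OR 2.59, by overall SVR:

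| Overall SVR | 50% | 60% | 70% | 80% | 84.0% | 90% | 94.3% |
|---|---|---|---|---|---|---|---|
| Power | 82.3% | 80.5% | 74.3% | 61.3% | 53.4% | 38.0% | about 24% |

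Power equals 80% at overall SVR of 38.8% and 61.2% and is higher only between them. Across the plan's own interval it never exceeds 53.4%.

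**Step 6: a rate that reproduces the stated figures.** With a reference-group SVR of 50%, OR 2.59 gives 50.0% against 72.1%, and m = 0.6107. The standard errors are 0.0796 (null) and 0.0775 (alternative). Power = Φ[(0.2214 − 1.96 × 0.0796)/0.0775] = Φ(0.84) = 80.0%. The ORs with 80% power at that rate are 2.588 and 0.386, which round to the stated 2.59 and 0.39.

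**Step 7: what the design can detect.** At 90% overall SVR and n = 75 per group, 80% power needs OR 6.13, or 1/6.13 = 0.163 (83.2% vs 96.8%). Exact chi-square gives 5.4 and Fisher 6.8. At 84.0% overall SVR the figure is 3.86, or 0.26. To keep OR 2.59 at 90% SVR:

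n per group = [1.96·√(2 × 0.09) + 0.842·√(0.8594 × 0.1406 + 0.9406 × 0.0594)]² / 0.0812² ≈ 213.2

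That rounds up to 214 per group, or 428 in total.

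**The case against.** The best defence is that the sentence is only an illustration, introduced by e.g., after a sample size justified by precision. Nothing shows that 150 was derived from it, and Section 5 presents 150 as an estimate of how many will be treated. The SVR12 interval is right. Factors associated with SVR12 also appear as Exploratory Objective 1, and no hypothesis about SVR12 predictors is stated. Treatment setting, the sentence's own example, is not among the factors Section 10 names, although that list may not be exhaustive.

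All of this stands and limits the consequence to a misleading statement, not a flawed design. It does not make the number right. Predictors of non-response are still written into the primary objective, and no other power figure supports that analysis.

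Two technical points also have force. First, the single figure of 38% depends on reading 90% as the overall rate with a two-sided test; the readings in Step 4 run from 28.9% to 65.2%, all below 80%. Second, the detectable OR of 6.1 is a normal approximation with only 75 × 0.032 = 2.4 expected non-responders in the better group, so it is best given with its range of 5.4 to 6.8.

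Finally, the documents do not say how 0.39 and 2.59 were obtained. A 50% default is an inference from the match in Step 6, and the conclusion does not rest on it.

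**Conclusion.** The concern holds. At the plan's 90% SVR, unadjusted power for an odds ratio of 2.59 is about 38%, not 80%, so such an effect would be missed about 6 times in 10. This rests on equal groups of 75, two-sided alpha 0.05, 90% as the overall rate and complete SVR12 data. Adjusted models or missing SVR12 results would in general lower power further. The error should be fixed, but it is confined to one sentence that appears twice.

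**What to change.** In Section 10 and in the Statistics row of the synopsis, delete the word *robust* and replace the power sentence with text such as:

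*At 90% overall SVR and 150 participants (75 in each group of an evenly split variable), an unadjusted two-sided 5% comparison of two proportions (normal approximation, pooled variance) has 80% power for an odds ratio of about 6.1 or 0.16 (about 83% vs 97%; 5.4 by exact chi-square, 6.8 by Fisher's test). Power for an odds ratio of 2.59 is about 38%.*

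No extra participants are needed, and the SVR12 estimate, its interval, the data collection and the regression analyses stay as they are. The only price is a less favourable stated power.

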Hypothesis 2.1: The incidence of HCV reinfection following successful elbasvir/grazoprevir therapy will be <8 per 100 p-yrs among people with recent injecting drug use or receiving OST.

Hypothesis 2.2: HCV reinfection will be associated with ongoing \geq daily injecting drug use, and needle and syringe borrowing. OST and high-coverage access to needle and syringes will be associated with reduced HCV reinfection.

Outcome: Incidence of HCV reinfection following successful elbasvir/grazoprevir therapy.

Statistical analysis: Rates of HCV reinfection will be calculated using person-time of observation. The estimated date of reinfection will be calculated as the midpoint between the dates of the last undetectable HCV RNA test and the first detectable HCV RNA test at the time of HCV reinfection. Time at risk will commence at the date of undetectable HCV RNA at end of treatment and end at the first of estimated date of re-infection, death, loss-to-follow up or end of study. Confidence intervals for rates will be calculated using a Poisson distribution.

Cox proportional hazards analyses (or other appropriate regression models) will be used to estimate crude and adjusted hazard ratios and corresponding 95%CI to evaluate factors associated with reinfection. Factors hypothesised to be associated with reinfection include demographic factors (age, sex), injecting behaviours (current injecting drug use, daily injecting, type of drug injected, injecting equipment borrowing), use of needle and syringe programs, and opioid substitution treatment with time-updated co-variables.

Sample Size: Overall, based on previous reports of HCV reinfection among current PWID³², and assuming loss to follow-up is 20% per year, it is estimated that the overall reinfection rate will be 8/100 p-yrs (95%CI 5.3, 11.4; 337 p-yrs of follow-up; 27 reinfections). Overall (135 with successful therapy, 27 reinfections), we will have 80% power to detect a hazards ratio (HR) of 2.94 or greater (with alpha=0.05) for a variable 50% prevalent (e.g. ongoing injecting drug use).

Collateral research

Evaluation of HCV phylogenetics

All participants enrolled in this study with available plasma samples at screening or baseline (HCV RNA detectable) will be sequenced for HCV RNA for evaluation of HCV phylogenetics.

Evaluation of HCV re-infection

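### Reinfection time at risk is not stopped at the last HCV RNA test and the date of loss is undefined, so untested time can pull the reinfection rate down

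*Combined protocol and SAP*

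**What the plan says.** All of this is in Section 10, Secondary Objective, unless noted.

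- **Start of the clock:** "Time at risk will commence at the date of undetectable HCV RNA at end of treatment".
- **End of the clock:** time at risk will "end at the first of estimated date of re-infection, death, loss-to-follow up or end of study".
- **Event date:** the "midpoint between the dates of the last undetectable HCV RNA test and the first detectable HCV RNA test".
- **Hypothesis 2.1:** reinfection incidence "will be <8 per 100 p-yrs among people with recent injecting drug use or receiving OST".
- **Planning figures:** "135 with successful therapy, 27 reinfections", an expected rate of "8/100 p-yrs (95%CI 5.3, 11.4; 337 p-yrs of follow-up; 27 reinfections", "assuming loss to follow-up is 20% per year".
- **Visits (Synopsis, Study design):** "Participants will be followed up every 3 months for the first year and every 6 months in year's 2-3". Section 6.1 places them at Weeks 24, 36, 48, 60, 84, 108, 132 and 156.

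No section stops person-time at the last HCV RNA test, and none says how the date of loss to follow-up is fixed.

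**The concern.** Numerator and denominator follow different rules. A reinfection enters the numerator only when a test detects it, and its person-time is bracketed by two tests. Event-free person-time has no such bracket at its far end. If a participant is tested, leaves the study untested and is dated as lost some weeks or months later, those weeks count as reinfection-free although nobody looked.

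The error has one direction: it adds to the denominator and never to the numerator. That direction favours Hypothesis 2.1. Visits in years 2-3 are 24 weeks apart, so an untested tail can be long, and the planned loss of 20% per year means that many participants could have one. Because the expected rate is itself 8, a small systematic shift is enough to move the point estimate to the other side of the benchmark.

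The Cox model uses the same follow-up times, so untested participants would stay in its risk sets as event-free. The time-updated behavioural covariates come from visit surveys and are equally unknown in that stretch.

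**Working it through.** **1. The plan's own figures.** 27 / 337 = 8.01 per 100 person-years, and 337 × 0.08 = 27.0 events, so rate and events agree. For the person-years, 135 × (1 + 0.8 + 0.64) = 329.4, within 3% of 337. The exact Poisson interval for 27 events in 337 person-years is 5.3 to 11.7. The stated upper limit of 11.4 fits an exact binomial interval on 27/337 (5.35 to 11.44) rather than the Poisson method the plan names. That is a side observation and does not affect this point.

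**2. Sensitivity on those figures.** Hold 27 events and treat 337 as tested time. Adding 10 untested person-years gives 27 / 347 = 7.78, and adding 20 gives 27 / 357 = 7.56. Each 10 untested person-years lowers the rate by about 0.2.

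**3. How much untested time to expect.** This was simulated.

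- From the plan: 135 responders, clock starting at Week 12, the Section 6.1 visit weeks, midpoint dating, 20% loss per year.
- Assumed: constant hazards for reinfection and loss, every visit attended and tested until loss, and loss independent of reinfection. An event counts only if a visit falls after infection and before loss.

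About 62 of the 135 are lost before Week 156. The rate is events divided by person-years.

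| True rate | Annual loss | Event-free time ends at | Events | Person-years | Rate per 100 |
|---|---|---|---|---|---|
| 8.0 | 20% | last test | 19.37 | 242.37 | 7.99 |
| 8.0 | 20% | true date of loss | 19.37 | 252.54 | 7.67 |
| 8.0 | 20% | first missed visit | 19.37 | 263.01 | 7.36 |
| 8.5 | 20% | last test | 20.49 | 241.11 | 8.50 |
| 8.5 | 20% | true date of loss | 20.49 | 251.23 | 8.16 |
| 8.5 | 20% | first missed visit | 20.49 | 261.62 | 7.83 |

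Censoring at the last test with midpoint dating returns the true rate, so the shift comes from the tail alone.

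**4. Lower loss.** At 10% per year the person-years are 286.0 (last test), 291.72 (date of loss) and 297.53 (first missed visit). Scaling the true rate by these gives 8.0 × 286.0 / 291.72 = 7.84 and 8.0 × 286.0 / 297.53 = 7.69.

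**5. Where the benchmark is crossed.** At 20% loss the inflation factors are 252.54 / 242.37 = 1.042 and 263.01 / 242.37 = 1.085. A true rate up to about 8 × 1.042 = 8.3 (date of loss) or 8 × 1.085 = 8.7 (first missed visit) would appear as below 8.

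**6. Limit of the simulation.** Its 242 to 263 person-years and 19 events do not match the plan's 337 and 27. It accrues loss continuously and removes reinfected participants from risk. Read it for the proportional shift, not as a forecast of the trial's totals.

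**The case against.** The strongest reply is that the plan never dates loss to follow-up, and that it bases rates on person-time under observation, which can be read as stopping at the last attended visit. Research plasma is scheduled at every post-treatment visit, so last visit and last test would coincide and the bias from loss would be zero. This stands as a possible reading. But the plan does not say it, and an analyst who uses the date contact ended or the first missed visit would also be following the text.

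Three stronger inferences are tempting, and the documents do not support them.

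- *That every end point in the rule is an untested date.* For a completer, end of study is the Week 156 visit, where Section 6.1 lists HCV RNA testing and research plasma. Those participants add no untested time.
- *That lost participants are carried to the end of the study.* The rule takes the first of the listed dates, so doing this would contradict it.
- *That the trial would wrongly pass a test against 8.* Section 10 plans a rate with a Poisson interval and a regression on predictors. It sets no test, margin or success criterion against the benchmark. Even the crossing of 8 depends on the reading: a true 8.5 shows as 7.8 with loss dated at the first missed visit, but as 8.2 at the true date of loss.

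It is also fair that the shift is small beside sampling error. That does not remove it: sampling error is shown in the interval and runs both ways, while this error appears in no interval and runs one way.

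**Conclusion.** The concern holds as a modest, one-directional weakness in a secondary analysis. As written, the rule lets untested time into the denominator unless loss happens to be dated at the last tested visit. Under the two ordinary datings of loss, a true 8.0 is reported as 7.7 or 7.4 at 20% annual loss (4% to 8% low), and as 7.8 or 7.7 at 10% loss. The sizes rest on the simulation's assumptions of full attendance until loss and loss unrelated to reinfection, and on a date of loss that the documents leave open. The direction rests on neither: time in which no event can be counted can only lower the rate. The rule is worth correcting because the planned rate equals the benchmark and the correction costs almost nothing. Any effect on the Cox hazard ratios depends on whether dropout differs by covariate, which the documents do not say.

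**What to change.** Replace the end-of-risk rule in Section 10 with:

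> Time at risk ends at the estimated date of reinfection or, in participants without reinfection, at the date of the last HCV RNA test (local or research plasma) on or before death, loss to follow-up or end of study.

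Use the same censoring date in the Cox model. Naming research plasma matters because the Schedule of Assessments marks local HCV RNA testing after the SVR12 visit as standard of care, while plasma is collected at every visit. A stored sample should count only once it has been tested.

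The cost is one sentence and, in the simulation, 252.54 − 242.37 = 10 to 263.01 − 242.37 = 21 person-years, in none of which an event could have been counted. With events unchanged, the Poisson limits rise in proportion, so the interval is about 4% to 9% wider on the rate scale. No new data are needed.
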